Virtual reality (VR) has emerged in plenty of domains as a promising tool for therapy and rehabilitation. Numerous studies adopted VR in improving cognitive behaviours in children

with ADHD; however, the focuses of these studies were cognitive functioning of daily living context, attentional performance and impulsivity. None of these studies utilised VR to improve social interaction competence and appropriateness in children with ADHD.

Furthermore, VR provides controllable immersive environments to engage children, sustain their attention and allow them to effectively gain skills in a safer environment. VR systems generally consist of a head-mounted display and screen so that the therapy can be conducted in a relatively low spatial limitation. Although no study has investigated VR social interaction skills in children with ADHD, evidence has proposed the use of VR social skill training in children with Autistic Spectrum Disorder (ASD). Most of the studies regarding children with ASD also used some real-life scenarios, for example, classrooms, transportation and supermarket, in their social skills training program. The differences in social skills between ADHD and ASD are that children with ADHD are easy to be distracted, avoid or dislike concentrating on one thing and are more likely to interrupt others' speaking; those with ASD are less aware of others around them, overly attached to one object that they like and hard to give meaning to their speech. Due to these discrepancies, the design of social VR intervention in this study will be put in more instantaneous events, objects and avatars in each scenario to improve the distraction problems of children with ADHD. In addition, social VR, which allows more than one user to appear as avatars in a lifelike environment and connect with other users in real-time, will be adopted in this study instead of VR to enhance engagement and interaction among children with ADHD.

Considering the prevalence and advantages of social VR, we plan to develop a social VR training program that contains three real-life scenarios and compare the effects of social VR training and traditional social skills training on social interaction skills, inhibitions, emotional control, behavioural and emotional difficulties and conduct disorders for children with ADHD in Hong Kong using receiving no training as a control.

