Cultivating sufficient and appropriate social interaction skills for children with ADHD is a vital step to assist them in integrating into the community. The real-life scenarios created by VR offer a more effective alternative to therapeutic strategies for children with ADHD. However, no previous study adopted social VR to assess social interaction competence and appropriateness in children with ADHD and no randomised controlled trial (RCT) compared the effectiveness of social VR training and traditional social skills training on enhancing the social interaction skills in children with ADHD. The traditional social skills training for

children with ADHD lacked the provision of real-life scenarios and was limited by time and space. Social VR allowing real-time connection and interaction between patients and the virtual instructor was absent in previous studies. To fill these research gaps, we proposed to conduct a three-arm RCT to answer the research question of whether social VR training has higher effectiveness than traditional social skills training in enhancing the social interaction skills of children with ADHD in Hong Kong. The findings of this study are expected to unveil the clinical impacts and compliance and acceptability of social VR training for enhancing social interaction skills among children with ADHD.

To fill these research gaps, we proposed to conduct a three-arm RCT to answer the research question of whether social VR training has higher effectiveness than traditional social skills training in enhancing the social interaction skills of children with ADHD in Hong Kong. The findings of this study are expected to unveil the clinical impacts and compliance and acceptability of social VR training for enhancing social interaction skills among children with ADHD.

Aims and hypotheses

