The study targets children with diagnosed ADHD and aims to (1) develop a social virtual reality-based intervention, (2) investigate its effects on improving the social skills and executive functioning of inhibitions, emotional control and attention of the children compared to traditional social skills training and (3) evaluate the subjects acceptability and compliance with social VR training for enhancing social interaction skills. It is hypothesised that the social interaction skills of the participants in the social VR training group are likely to perform better than those in the traditional social skills training group. Participants in the waitlist control group will receive no change in social interaction skills compared with the two intervention groups.

Methods/ Design

The study will be a three-arm randomised controlled trial comparing the effects of a social VR-based intervention with traditional social skills training on social skills and executive functioning of children with ADHD. Participants in the social VR intervention group and traditional social skill training group will receive 12 training sessions for 3 weeks (4 sessions per week), and participants in the waitlist control group will be asked to retain their usual lifestyles for 3 weeks. The overall design of the study is illustrated in Figure 1. Ethical

approval for the study has been obtained by the Human Subjects Ethics Application Review Committee of The Hong Kong Polytechnic University.

[figure not shown]

Figure 1. Study design

Participants

Individuals who meet the inclusion criteria will be recruited. The criteria are as follows: 1) aged between 6 and 12 years; 2) ethnic Chinese; 3) residing in Hong Kong; 4) having received a diagnosis of ADHD by Child Assessment Service in Hong Kong or via private practice; 5) stable on pharmacological and/or psychological treatment for ADHD 8 weeks before baseline (determined by health care professionals on the basis of medication data and behavioural observation); 6) no initiation or change of pharmacological treatment for ADHD during the intervention period; 7) ability to read Chinese, and speak and listen to Cantonese by the child and by at least one of their parents or legal guardian; 8) willing to provide informed consent by both participants and one of their parents or legal guardian.

Exclusion criteria are as follows: 1) comorbid autism; 2) mental retardation; 3) an estimated

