All statistical analyses will be performed in SPSS version 26.0 software (IBM Corp, Armonk, NY, USA) and are two-sided with a level of significance of < 0.05 . Demographic information of the participants will be summarised with frequency and percentage for categorical variables. The continuous variables will be summarised by mean and standard deviation. The change between baseline and week 3 within each arm will be tested using t-tests. To examine the between-group difference in terms of measure outcomes from baseline to week 3, repeated analyses of covariance (ANCOVA) with adjustment of baseline characteristics will be conducted. To evaluate the improvement during the intervention period among the three groups, f-tests will be performed on primary and secondary outcome measures at the beginning of the first session and at the end of the last session. An intention-to-treat analysis will be performed. This analysis is regarded as the most appropriate approach to analyse RCT data by the highest-quality journals, which have utilised the CONSORT standard.

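### The analysis plan does not commit to estimating social VR minus traditional training, which is the trial's stated effectiveness question, and the three-group F-test cannot stand in for that contrast.

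*Combined protocol and SAP*

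**What the plan says.** The rationale, just before Aims and hypotheses, asks "whether social VR training has higher effectiveness than traditional social skills training in enhancing the social interaction skills". The first hypothesis in Aims and hypotheses is that social interaction skills of participants "in the social VR training group are likely to perform better than those in the traditional social skills training group". The waitlist has a stated role too. The background describes the comparison of the two trainings as "using receiving no training as a control", and the second hypothesis is "Participants in the waitlist control group will receive no change in social interaction skills compared with the two intervention groups".

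The Statistical analysis plan is one paragraph with three inferential procedures:

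- Within arms: "The change between baseline and week 3 within each arm will be tested using t-tests".
- Between arms: "To examine the between-group difference in terms of measure outcomes from baseline to week 3, repeated analyses of covariance (ANCOVA"). Its covariates are described only by the phrase "with adjustment of baseline characteristics will be conducted".
- Across all arms: "To evaluate the improvement during the intervention period among the three groups, f-tests will be performed on primary and secondary outcome measures".

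It also states two-sided testing at 0.05 and an intention-to-treat analysis. Process evaluation is the primary outcome. The SSRS-P and BRIEF are secondary, and parents score both before the first session and after the last.

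**The concern.** The effectiveness question concerns one pair of arms, but none of the three procedures is tied to that pair. The t-tests look inside each arm and do not compare arms. The F-tests involve all three arms, so a difference between training and no training can make them significant when the two trainings are equal. The ANCOVA could deliver the contrast, but the plan states neither the pair of arms nor an estimate with an interval. It also leaves open whether a score's own baseline is a covariate or, as the word repeated suggests, one of two outcome time points.

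The trial could therefore report significant results and have no planned estimate of how much better or worse VR is than traditional training. The pair of arms, the covariates and the SSRS-P score could then be chosen after the data are seen.

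**Working it through.** **Inputs from the documents.** Three arms of 30 (3 × 30 = 90), 15% attrition (Sample size); two-sided 0.05 (Statistical analysis plan).

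**The plan's own figure.** Sample size gives no power calculation, so 90 cannot be derived from an effect size. It cites a pilot minimum of 16 per group. With 15% attrition that is 16 / 0.85 = 18.8, or 19 per arm and 57 in total. The planned 90 exceeds this, as the section says. Expected completers are 30 × 0.85 = 25.5 per arm, taken as 25 below.

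**Assumptions, not in the documents.** The correlation r between baseline and week-3 score, and all effect sizes. The SD of the score is set to 1 at both times.

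**1. Can the F-test answer the question?** Let both trainings give the same mean change and the waitlist none. Take a change of 0.4 in units of the SD of change, with r = 0.6. The SD of change is √(2(1 − 0.6)) = 0.894, so the mean change is δ = 0.4 × 0.894 = 0.358 score SD. With own-baseline adjustment the noncentrality of the three-group F-test is

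λ = n × (2/3) × δ² / (1 − r²) = 30 × 0.667 × 0.128 / 0.64 = 4.0.

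The critical F(2, 86) is 3.10, which gives a probability of significance of 0.403. A simulation of 20,000 trials gave 0.402, and 0.360 for a significant F with no significant VR-minus-traditional difference.

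On change scores, λ = 30 × 0.667 × 0.128 / 0.80 = 3.2 and the probability is 0.330 (simulated 0.331, and 0.288 with no significant contrast).

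The result depends on the assumed change (adjusted F, 30 per arm, r = 0.6):

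| Standardised change in both trainings | F significant | F significant, VR minus traditional not |
|---|---|---|
| 0.2 | 0.129 | 0.096 |
| 0.4 | 0.402 | 0.360 |
| 0.6 | 0.752 | 0.705 |

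At 25 per arm and a change of 0.4 the figures are 0.337 and 0.294.

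**2. What does own-baseline adjustment add?** Standard error of VR minus traditional, in score SDs:

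- ANCOVA on own baseline: √(2/n) × √(1 − r²), df = 3n − 4.
- Change score (the group-by-time contrast of a two-time repeated analysis): √(2/n) × √(2(1 − r)), df = 3n − 3.

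Example, n = 30 and r = 0.5: √(2/30) = 0.258. ANCOVA: 0.258 × 0.866 = 0.224. Change score: 0.258 × 1 = 0.258. Power is from the noncentral t distribution for a true difference of 0.5 SD; the half-width is that of the 95% CI.

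| r (n = 30) | Change SE | ANCOVA SE | Change power | ANCOVA power | Change half-width | ANCOVA half-width |
|---|---|---|---|---|---|---|
| 0.3 | 0.306 | 0.246 | 36.7% | 51.9% | 0.61 | 0.49 |
| 0.5 | 0.258 | 0.224 | 48.2% | 59.9% | 0.51 | 0.44 |
| 0.6 | 0.231 | 0.207 | 57.2% | 66.8% | 0.46 | 0.41 |
| 0.7 | 0.200 | 0.184 | 69.6% | 76.5% | 0.40 | 0.37 |
| 0.8 | 0.163 | 0.155 | 85.7% | 89.1% | 0.32 | 0.31 |

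The gain falls from about 15 points at r = 0.3 to about 3 at r = 0.8. ANCOVA power reaches 80% at about r = 0.73. At 25 per arm, power is 41.5% against 52.1% (r = 0.5) and 61.5% against 68.5% (r = 0.7), and ANCOVA reaches 80% at about r = 0.78.

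**The case against.** The best defence is that the plan is under-specified rather than wrong. The second aim already names traditional training as the comparator. The ANCOVA sentence is separate from the three-group F-test sentence, so it is natural to read the ANCOVA as serving the between-arm aims. Baseline characteristics may well include the baseline score. The trial is sized as a pilot, and the efficacy scores are secondary.

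Much of this stands. The ANCOVA could yield the contrast, and if own-baseline adjustment is already meant the precision gain is zero. What remains is that no section commits to the pair of arms or to an interval, and a pilot has particular need of an interval.

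Two stronger readings are tempting and are not supported. A reader might infer that VR will be called superior because its within-arm test is significant and the traditional arm's is not, or that the F-test will be read as VR versus traditional. The plan states neither inference. The F-test figures show only why that test cannot replace the contrast. A reader might also infer that the waitlist comparisons are misplaced, but the background and the second hypothesis give them a purpose.

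A fair reservation about the remedy is that the protocol ranks no secondary outcome, so putting the SSRS-P first is a choice. It is the parent-rated scale that measures social skills directly.

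**Conclusion.** The point holds as a gap between the stated effectiveness question and the planned analysis, and it should be fixed. Followed as written, the plan need not estimate VR minus traditional training. With equally effective trainings, the three-group F-test is significant in about 40% of trials, and in about 36% it is significant with no significant difference between them (assumed standardised change 0.4, r = 0.6, 30 per arm).

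The precision gain is conditional. For an assumed 0.5 SD difference at 30 per arm it is about 15 points of power at r = 0.3, 12 at r = 0.5, 7 at r = 0.7 and 3 at r = 0.8, all against a change-score analysis. It is zero if the plan already intends own-baseline adjustment. The documents give no correlation or numerical effect size, so none of these figures is a property of this trial.

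A reader might infer that the trial's main result is in doubt. It is not: the primary outcome is process evaluation, which this does not touch.

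**What to change.** For the secondary effectiveness scores taken before the first and after the last session (SSRS-P and BRIEF), replace the repeated ANCOVA and the three-group F-test as the main comparison with an ANCOVA of the week-3 score on arm plus that score's own baseline. List any other covariates by name. Then:

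- Report the adjusted VR-minus-traditional difference on the SSRS-P with its 95% CI as the key effectiveness contrast. State which SSRS-P score is meant, since the protocol describes three subscales and designates none for this comparison.
- Report each training versus waitlist second.
- Treat within-arm changes as descriptive.
- Keep the process measures primary and analyse participants as randomised. Because the model needs a week-3 score, say how missing ones are handled; the plan is silent on this.

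The cost is a short rewrite of the Statistical analysis plan, with no added visit or measure. The downside is fewer p-values. At a 0.5 SD difference and 30 per arm, the contrast has under 80% power below about r = 0.73, so it should be read as an estimate with its interval rather than as a pass-or-fail test.

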Social VR intervention is developed to enhance the social interaction skills of children. The participants will wear a head-mounted display (HMD) for the Social VR intervention. Each session of the Social VR intervention lasts for a maximum of 20 minutes to ensure the participants focus on the intervention and prevent causing any physical effect. The duration will be adjusted depending on the emotion of the participants during the intervention. The Social VR intervention will mainly help the participant to enhance their social interaction skills and executive function. The intervention contains three real-life virtual scenarios, including (1) classroom and playground, (2) MTR station and compartment, and (3) street and building. One scenario will be adopted in each session. The sequences of the scenarios used in each session will be the same for all participants. During the Social VR intervention, one RA will also appear as one avatar in the scenario to guide the participants to complete a series of tasks. Each intervention session will be conducted in a classroom independently for each participant.

Traditional social skills training

An experienced SEN teacher will teach the participants social interaction skills through tradidactic instructions and role-play activities. Four modules will be covered in the 3-week training: (1) how to introduce yourself and basic social skills; (2) how to listen to others; (3) how to share with others; (4) learn to know how people feel and how to empathise. These modules have been applied in many studies. The content of this training will be as similar as possible to the Social VR training. The training lasts 20 minutes which depends on the emotion of the participants. Each training session will be conducted in a classroom independently for each participant.

Waitlist control group

The participants in this group will receive no training and they can participate in the social VR training after the intervention period. To ensure consistency of the experiment, the participants are not allowed to initiate or change their pharmacological treatment during the 3-week intervention period.

Measures

Questionnaires

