The parents or legal guardians of the participants will complete a structured questionnaire at the baseline and after the last session. Demographic information, including age, gender, Medication, ADHD symptoms and game experience will be recorded at the baseline. The questionnaires include questions about social skills and executive functioning. The satisfaction of the participants and their parents or legal guardians towards the training program will be assessed at week 3. The VR sickness of the participant will be evaluated after each session. The assessor will be blind to the treatment condition. The questionnaires will include the following scales:

Primary outcome measure

1. Process evaluation

The process evaluation of the training will be assessed by investigating: (i) training acceptability as measured by the participants' attendance and compliance; (ii) recruitment rate; (iii) participant completion.

(i) Assessment of training acceptability and compliance

The attendance of the participants during the trainings will be recorded. To verify the validity of the findings, training non-adherence of the participants will be terminated which will be stated in the consent form. The absence of any training session will be considered as non-adherence. The participants will be asked about their willingness of partaking in this kind of training by one 7-point Likert scale question which is used to reflect the acceptability to the intervention. The retention rate should be at least 85% according to the feasibility RCT.

The compliance with the training program will be evaluated by the communication log which the parents record their children's daily activity and emotion in the 3-week intervention period. The participants' parents will be reminded to attend the training through telephone in the first four training sessions and WhatsApp or WeChat in the fifth and eighth training sessions. No reminder follow-up will be made in the remaining four sessions. These data will be used to evaluate their compliance.

(ii) Recruitment rate

The recruitment rate is at least 48.5% of all referrals according to the feasibility study.

(iii) Participant completion

Participants attending at least nine (i.e., 75%) of the 12 sessions are considered to have completed the program.

Secondary outcome measure

1. Social Skills Rating Scale (SSRS-P)

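### Two attendance rules in the primary process evaluation contradict each other, follow-up of terminated children is not stated, and the baseline score is not named as a covariate

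*Combined protocol and SAP*

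**What the plan says.** All references are to the combined protocol and SAP.

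- **Termination.** Under Primary outcome measure, (i) Assessment of training acceptability and compliance: "The absence of any training session will be considered as non-adherence", and "training non-adherence of the participants will be terminated which will be stated in the consent form". The same subsection sets a retention target of at least 85%.
- **Completion.** Under (iii) Participant completion: "Participants attending at least nine (i.e., 75%) of the 12 sessions are considered to have completed the program".
- **Waitlist.** Under Waitlist control group: "The participants in this group will receive no training" (training is offered to them only after the intervention period).
- **Analysis set.** Under Statistical analysis plan: "An intention-to-treat analysis will be performed". The set is not defined further and no missing-data method is given. For withdrawals, the safety section provides only for recording the reason.
- **Between-group analysis.** For differences from baseline to week 3, "repeated analyses of covariance (ANCOVA) with adjustment of baseline characteristics will be conducted". The section adds that "f-tests will be performed on primary and secondary outcome measures at the beginning of the first session" and again at the end of the last one, to evaluate improvement among the three groups.
- **Baseline data.** Under Questionnaires: "Demographic information, including age, gender, Medication, ADHD symptoms and game experience will be recorded at the baseline". Parents score SSRS-P and the two BRIEF subscales before the first and after the last session, so baseline scores will exist. They are not in that list and are not named as covariates anywhere.

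**The concern.** There are three linked issues.

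1. The two attendance statements give different answers for the same child. Attendance, retention and completion are the primary outcomes of this pilot, so the headline feasibility result depends on which statement is operated.
2. Only the two trained arms have sessions to miss, so termination for absence can occur only there. If week-3 scores are not sought from terminated children, data are lost from the trained arms and not from waitlist, and the comparisons with waitlist could be biased.
3. If baseline enters the repeated model only as a time point, the group-by-time test is a comparison of change scores. Under randomisation it is valid, but it uses the collected baseline less efficiently than an ANCOVA on that score. The social VR versus traditional training hypothesis in Aims and hypotheses would then have a wider interval than necessary. With a repeated ANCOVA and F-tests both planned, the text also does not say which result answers that hypothesis.

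**Working it through.** **Attendance rules**

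The plan's own figure first: 9/12 = 0.75, so the stated 75% is correct.

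Let m be the sessions missed out of 12. Termination applies when m ≥ 1; completion applies when m ≤ 3. Both hold for m = 1, 2 or 3, that is, 11, 10 or 9 sessions attended.

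If termination follows the first absence, at session k, the child has attended k − 1 sessions. Completion needs k − 1 ≥ 9, so k ≥ 10. The child must attend all of the first nine sessions.

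The documents give no expected attendance. Take a per-session probability p, independent across sessions (assumed). Completion without termination is P(Binomial(12, p) ≥ 9). With termination at first absence it is p^9. The share meeting both statements when nobody is stopped is P(9 to 11 sessions).

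| p | Completion, no termination | Completion, termination at first absence (p^9) | Share with 9–11 sessions |
|---|---|---|---|
| 0.90 | 97.4% | 38.7% | 69% |
| 0.95 | 99.8% | 63.0% | 46% |
| 0.98 | 99.99% | 83.4% | 21% |
| 0.99 | 100.0% | 91.4% | 11% |

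At p = 0.95, the last column is about 27 of the 60 trained children.

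Retention: if termination counts as non-retention (not stated), the 85% target needs p^12 ≥ 0.85, so p ≥ 0.85^(1/12) = 0.987. At p = 0.95, p^12 = 0.54.

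**Missing week-3 scores**

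Shift in an arm's mean = share lost × difference between lost and retained children. Assume that no waitlist child is lost.

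- 15% lost (the attrition figure under Sample size), assumed difference 0.25 or 0.5 SD: 0.15 × 0.25 = 0.04 SD; 0.15 × 0.5 = 0.08 SD (0.0375 and 0.075 before rounding).
- If every child with an absence were lost, at p = 0.95: 1 − 0.54 = 0.46, and 0.46 × 0.5 = 0.23 SD.
- Social VR minus traditional, with equal loss and equal difference: (0.15 − 0.15) × 0.5 = 0.

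**Baseline score as covariate**

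Let rho be the correlation of the baseline and week-3 scores. It is not given, so 0.3, 0.5 and 0.7 are assumed. Per-child variances in units of the score variance are: change score 2(1 − rho); last session alone 1; ANCOVA on the baseline score 1 − rho².

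| Ratio to ANCOVA | rho 0.3 | rho 0.5 | rho 0.7 |
|---|---|---|---|
| Change score, 2/(1 + rho) | 1.54 | 1.33 | 1.18 |
| Change score with another covariate correlated r = 0.5 (assumed) with baseline, [2 − r²(1 − rho)]/(1 + rho) | 1.40 | 1.25 | 1.13 |
| Last session unadjusted, 1/(1 − rho²) | 1.10 | 1.33 | 1.96 |
| Baseline score already included | 1 | 1 | 1 |

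The second row covers a covariate such as baseline ADHD symptoms, taken to relate to week 3 only through the baseline score.

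At rho = 0.5 with 25 per arm (30 × 0.85 = 25.5, rounded down), the 95% CI half-width is 0.57 SD for change score and 0.49 SD for ANCOVA. The change-score analysis is worth 25/1.333 = 18.75, about 19 per arm. Power for an assumed 0.5 SD difference is 41% against 52%.

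**The case against.** **The covariate may already be there.** The plan specifies ANCOVA with baseline adjustment, and the scales are completed in the same parent questionnaire that collects the demographics. A reader might infer that the plan omits the baseline score. It does not say so; it lists no covariates. This stands: the precision loss is conditional, and it is not bias.

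**The F-test sentence has two readings.** It can mean separate tests at the first and last sessions. Its stated purpose is to evaluate improvement, which needs both time points, so it can equally describe a group-by-time test. The last-session row in the working applies only to the first reading.

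**Conflict with intention-to-treat.** A reader might infer that the attendance rules breach it. The nine-session threshold is a feasibility definition and has no bearing on the analysis set. Termination would breach intention-to-treat only if terminated children were not assessed or were excluded, and the documents say neither; termination may mean training only. What remains is silence, with outcomes timed after the last session and no missing-data method.

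**Bias between the trained arms.** The same rule applies to both, so by itself it creates no imbalance between social VR and traditional training.

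**Stakes.** SSRS-P and BRIEF are secondary, the trial is sized by pilot guidance, and ANCOVA does not make the comparison decisive. The hypothesis names no instrument, and the psychiatrist's task score also bears on it. All this is fair for the covariate point. It does not reach the attendance contradiction, which sits inside the primary outcomes.

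**Conclusion.** The attendance contradiction is established from the text, and it affects the primary process outcomes. Its size depends on attendance, which the documents do not predict: at an assumed independent 95% per session, completion is about 99.8% or about 63%. Real absences tend to cluster within children. For the same average attendance, that raises the share attending the first nine sessions, so the gap is illustrative and probably smaller in practice.

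Follow-up of terminated children is a gap in the plan and a risk to the waitlist comparisons. The shift is 0.04 to 0.08 SD at 15% one-sided loss under the assumed differences, and more if losses are heavier.

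The covariate point is an under-specification. The cost is none if the baseline score is included, and a variance ratio of 1.18 to 1.54 over the assumed correlations if the test is a plain change-score comparison.

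The sponsor should correct all three. None invalidates the randomised comparison, and none changes N = 90.

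**What to change.** 1. Reconcile the any-absence termination statement with the nine-of-12 completion statement, and say how termination counts towards retention. Which attendance rule applies is for the sponsor to decide.
2. Whatever the reconciled rule, seek week-3 parent scores from every randomised child, including those who stop training, and analyse them in the allocated arm.
3. For SSRS-P and each of the two BRIEF subscales, state one between-group model: week-3 score on arm plus the baseline value of the same score. Report the social VR minus traditional difference with its 95% CI. List any further covariates by name.
4. Say what the F-tests are. If a separate first-session test is intended, replace it with baseline means and SDs by arm, because after randomisation it tests only chance differences.

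Cost: SAP wording and one follow-up contact with the parents of each child who stops training. A consent-form change with ethics notification may also be needed, because the termination rule is to appear in the consent form and approval has already been obtained. No new measures and no change in sample size.
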